**Comprehensive Adverse Events and Potential Risks List**

The Comprehensive Adverse Events and Potential Risks list (CAEPR) provides a single list of reported and/or potential adverse events (AE) associated with an agent using a uniform presentation of events by body system. In addition to the comprehensive list, a subset, the Specific Protocol Exceptions to Expedited Reporting (SPEER), appears in a separate column and is identified with bold and italicized text. Refer to the 'CTEP, NCI Guidelines: Adverse Event Reporting Requirements' [http://ctep.cancer.gov/protocolDevelopment/electronic\\_applications/docs/aeguidelines.pdf](http://ctep.cancer.gov/protocolDevelopment/electronic_applications/docs/aeguidelines.pdf) for further clarification. *Frequency is provided based on 2678 patients.* Below is the CAEPR for Ipilimumab (MDX-010).

Rev. 2/12

Rev. 2/12

**NOTE:** FOR THIS PROTOCOL, events listed in the SPEER column should be considered EXPECTED if the grade being reported is the same or lower than the grade noted in the parentheses next to the AE in the SPEER. Events listed in the SPEER column should be considered UNEXPECTED if the grade being reported exceeds the grade noted in parentheses next to the AE in the SPEER.

Rev. 10/14

**Version 2.7, June 28, 2015**

Adverse Events with Possible Relationship to Ipilimumab (MDX-010) (CTCAE 4.0 Term) [n= 2678]			Specific Protocol Exceptions to Expedited Reporting (SPEER)
Likely (>20%)	Less Likely (<=20%)	Rare but Serious (<3%)	
BLOOD AND LYMPHATIC SYSTEM DISORDERS			
		Blood and lymphatic system disorders - Other (acquired hemophilia)	
CARDIAC DISORDERS			
	Atrial fibrillation		
		Myocarditis 	
EAR AND LABYRINTH DISORDERS			
	Hearing impaired		
ENDOCRINE DISORDERS			
	Adrenal insufficiency 		
	Endocrine disorders - Other (hypopituitarism/hypophysitis) 		
	Endocrine disorders - Other (testosterone deficiency) 		
	Hyperthyroidism 		
	Hypothyroidism 		

Adverse Events with Possible Relationship to Ipilimumab (MDX-010) (CTCAE 4.0 Term) [n= 2678]			Specific Protocol Exceptions to Expedited Reporting (SPEER)
Likely (>20%)	Less Likely (<=20%)	Rare but Serious (<3%)	
EYE DISORDERS			
	Eye disorders - Other (episcleritis) 		
	Uveitis 		
GASTROINTESTINAL DISORDERS			
	Abdominal pain		
	Colitis 		Colitis (Gr 3)
		Colonic perforation 	
	Constipation		
Diarrhea			Diarrhea (Gr 3)
	Enterocolitis		
	Esophagitis		
		Ileus	
Nausea			Nausea (Gr 3)
	Pancreatitis 		
	Vomiting		
GENERAL DISORDERS AND ADMINISTRATION SITE CONDITIONS			
	Chills		
Fatigue			Fatigue (Gr 3)
	Fever		Fever (Gr 2)
	Infusion related reaction		
		Multi-organ failure	
HEPATOBIILIARY DISORDERS			
	Hepatobiliary disorders - Other (hepatitis) 		
IMMUNE SYSTEM DISORDERS			
	Autoimmune disorder 		
		Immune system disorders - Other (GVHD in the setting of allotransplant)	
INFECTIIONS AND INFESTATIONS			
	Infections and infestations - Other (aseptic meningitis) 		
INVESTIGATIONS			
	Alanine aminotransferase increased		
	Aspartate aminotransferase increased		
	Neutrophil count decreased		

Adverse Events with Possible Relationship to Ipilimumab (MDX-010) (CTCAE 4.0 Term) [n= 2678]			Specific Protocol Exceptions to Expedited Reporting (SPEER)
Likely (>20%)	Less Likely (<=20%)	Rare but Serious (<3%)	
METABOLISM AND NUTRITION DISORDERS			
	Anorexia		
	Dehydration		
	Hyperglycemia		
MUSCULOSKELETAL AND CONNECTIVE TISSUE DISORDERS			
	Arthralgia		
	Arthritis		
	Musculoskeletal and connective tissue disorder - Other (polymyositis) 		
NERVOUS SYSTEM DISORDERS			
	Facial nerve disorder		
	Headache		
	Nervous system disorders - Other (Guillain-Barre syndrome) 		
	Nervous system disorders - Other (myasthenia gravis) 		
	Trigeminal nerve disorder		
RENAL AND URINARY DISORDERS			
	Acute kidney injury		
	Renal and urinary disorders - Other (granulomatous tubulointerstitial nephritis)		
RESPIRATORY, THORACIC AND MEDIASTINAL DISORDERS			
	Pneumonitis		
SKIN AND SUBCUTANEOUS TISSUE DISORDERS			
		Erythema multiforme	
	Pruritus		Pruritus (Gr 3)
Rash maculo-papular			Rash maculo-papular (Gr 3)
	Skin and subcutaneous disorders - Other (Sweet's Syndrome)		
		Stevens-Johnson syndrome	
		Toxic epidermal necrolysis	
	Urticaria		
VASCULAR DISORDERS			
	Hypotension		

 This table will be updated as the toxicity profile of the agent is revised. Updates will be distributed to all Principal Investigators at the time of revision. The current version can be obtained by contacting [contact]. Your name, the name of the investigator, the protocol and the agent should be included in the e-mail.

-  Ipilimumab can result in severe and fatal immune-mediated adverse events probably due to T-cell activation and proliferation. These can include (but are not limited to) autoimmune hemolytic anemia, acquired anti-factor VIII immune response, autoimmune aseptic meningitis, autoimmune hepatitis, autoimmune thyroiditis, hepatic failure, pure red cell aplasia, pancreatitis, ulcerative and hemorrhagic colitis, endocrine disorders (e.g., autoimmune thyroiditis, hyperthyroidism, hypothyroidism, autoimmune hypophysitis/hypopituitarism, and adrenal insufficiency), ocular manifestations (e.g., uveitis, iritis, conjunctivitis, blepharitis, and episcleritis), sarcoid granuloma, myasthenia gravis, polymyositis, and Guillain-Barre syndrome. The majority of these reactions manifested early during treatment; however, a minority occurred weeks to months after discontinuation of ipilimumab especially with the initiation of additional treatments.
-  Late bowel perforations have been noted in patients receiving MDX-010 (ipilimumab) in association with subsequent IL-2 therapy.
-  In rare cases diplopia (double vision) has occurred as a result of muscle weakness (Myasthenia gravis).
-  Gastrointestinal hemorrhage includes Anal hemorrhage, Cecal hemorrhage, Colonic hemorrhage, Duodenal hemorrhage, Esophageal hemorrhage, Esophageal varices hemorrhage, Gastric hemorrhage, Hemorrhoidal hemorrhage, Ileal hemorrhage, Intra-abdominal hemorrhage, Jejunal hemorrhage, Lower gastrointestinal hemorrhage, Oral hemorrhage, Pancreatic hemorrhage, Rectal hemorrhage, Retroperitoneal hemorrhage, and Upper gastrointestinal hemorrhage under the GASTROINTESTINAL DISORDERS SOC
-  Infection includes all 75 sites of infection under the INFECTIONS AND INFESTATIONS SOC.

**Adverse events reported on Ipilimumab (MDX-010) trials, but for which there is insufficient evidence to suggest that there was a reasonable possibility that Ipilimumab (MDX-010) caused the adverse event:**

**BLOOD AND LYMPHATIC SYSTEM DISORDERS** - Anemia; Blood and lymphatic system disorders - Other (pure red cell aplasia); Febrile neutropenia

**CARDIAC DISORDERS** - Conduction disorder; Restrictive cardiomyopathy

**EYE DISORDERS** - Extraocular muscle paresis; Eye disorders - Other (retinal pigment changes)

**GASTROINTESTINAL DISORDERS** - Dyspepsia; Dysphagia; Gastrointestinal hemorrhage

**GENERAL DISORDERS AND ADMINISTRATION SITE CONDITIONS** - Flu like symptoms; Non-cardiac chest pain

**HEPATOBIILIARY DISORDERS** - Hepatic failure

**IMMUNE SYSTEM DISORDERS** - Allergic reaction

**INFECTIONS AND INFESTATIONS** - Infection

**INVESTIGATIONS** - Creatinine increased; Investigations - Other (rheumatoid factor); Lipase increased; Platelet count decreased; Serum amylase increased; Weight loss; White blood cell decreased

**METABOLISM AND NUTRITION DISORDERS** - Metabolism and nutrition disorders - Other (exacerbation of pre-existing diabetes mellitus)

**MUSCULOSKELETAL AND CONNECTIVE TISSUE DISORDERS** - Back pain; Joint range of motion decreased; Myalgia; Pain in extremity

**NEOPLASMS BENIGN, MALIGNANT AND UNSPECIFIED (INCL CYSTS AND POLYPS)** - Tumor pain

**NERVOUS SYSTEM DISORDERS** - Dizziness; Dysphasia; Ischemia cerebrovascular; Peripheral motor neuropathy; Peripheral sensory neuropathy; Seizure

**PSYCHIATRIC DISORDERS** - Anxiety; Confusion; Depression; Insomnia

**RENAL AND URINARY DISORDERS** - Proteinuria

**RESPIRATORY, THORACIC AND MEDIASTINAL DISORDERS** - Allergic rhinitis; Cough; Dyspnea; Laryngospasm

**SKIN AND SUBCUTANEOUS TISSUE DISORDERS** - Alopecia, Dry skin; Hyperhidrosis; Skin hypopigmentation

**VASCULAR DISORDERS** - Flushing; Hypertension; Vascular disorders - Other (temporal arteritis)

**NOTE:** Ipilimumab (MDX-010) in combination with other agents could cause an exacerbation of any adverse event currently known to be caused by the other agent, or the combination may result in events never previously associated with either agent.

## 5.5 Dose Modifications

All toxicities should be graded according to the NCI Common Terminology Criteria for Adverse Events (CTCAE) version 4.0.

All appropriate treatment areas should have access to a copy of the CTCAE version 4.0. A copy of the CTCAE version 4.0 can be downloaded from the CTEP web site (<http://ctep.cancer.gov>).

Rev. 11/13  
9/14

**NOTE:** Per Addendum #7, the dose modification plan for Arms A and D (ipilimumab 10 mg/kg) has been modified to become stricter due to a higher incidence of severe toxicities observed on Arms A and D than seen in Arms C and F. Arms C and F dose modification guidelines continue to be the same, with minor changes.

Rev. 2/12, 11/13  
9/14

### 5.5.1 ARMS A and D and Arms C and F: Patients Receiving Ipilimumab

#### 5.5.1.1 **Dose and Schedule Modifications for Arms A and D (Ipilimumab 10 mg/kg)**

There will be no dose reductions for ipilimumab. The dose of ipilimumab will either be given or delayed/discontinued. Patients may develop study drug-related toxicities that may require skipping doses or dose discontinuation. Some of these adverse events may be consistent with potentially drug-related immune-mediated phenomena; termed IRAEs ([Appendix XIII-Appendix XVII](#)). Details of how to dose study medication in the presence of adverse drug reactions that may or may not be IRAEs are addressed below.

Patients will delay or discontinue treatment with ipilimumab if they experience at least one adverse event, specified below, considered by the investigator to be **certainly**, **probably**, or **possibly** related to ipilimumab treatment unless otherwise specified. The following criteria will be used to determine dosing delay, restarting doses, or discontinuing ipilimumab. For an adverse event, review the following criteria in a stepwise manner: First, assess the dose delay criteria and decide whether a scheduled dose should be delayed. Second, determine whether the permanent discontinuation criteria apply to the adverse event in question as well.

**NOTE:** Due to the possible effect of treatment with ipilimumab on the immunologic response to infectious disease vaccines, patients must not have had any infectious disease vaccination (e.g., standard influenza, H1N1 influenza, pneumococcal, meningococcal, tetanus toxoid) 4 weeks before or after any dose of ipilimumab.

5.5.1.1.1 **Criteria to delay/skip one dose of ipilimumab on Arms A or D (ipilimumab 10 mg/kg)**

Delay ipilimumab dosing for any of the following certainly, probably, or possibly treatment related adverse events, unless otherwise specified:

- Grade  $\geq$  1 diarrhea and/or colitis **regardless of attribution**. Grade  $\geq$  2 diarrhea and/or colitis, certainly, probably, or possibly related to ipilimumab, requires permanent discontinuation (Section [5.5.1.1.3](#)).
- Any other  $\geq$  Grade 2 non-skin related adverse event (including IRAEs) except for laboratory abnormalities.
- Grade  $\geq$  2 laboratory abnormalities that are secondary to an immune-related adverse event or autoimmune phenomenon (e.g., Grade  $\geq$  2 TSH associated with a CTCAE v.4 grade 2 thyroid dysfunction induced by ipilimumab, anemia, neutropenia, amylase, lipase, CPK, hyperglycemia, or elevated LFTs) should also lead to an ipilimumab dosing delay/skipping.
- Any other  $\geq$  Grade 3 laboratory abnormality.
- Any  $\geq$  Grade 3 skin-related adverse event (including IRAEs) **regardless of attribution**.

5.5.1.1.2 **Criteria to resume ipilimumab treatment on Arms A or D (ipilimumab 10mg/kg)**

Ipilimumab **may not** be restarted while the patient is being treated with oral or intravenous corticosteroids for the management of immune related adverse events except for patients on stable doses of hormone replacement therapy for adrenal insufficiency such as hydrocortisone. In addition, patients must be off and have no requirement for oral/I.V. corticosteroids for at least 1 week and meet the other criteria for retreatment as outlined below.

Restart ipilimumab dosing if/when the adverse event(s) resolve(s) to  $\leq$  Grade 1

Rev. 2/14

severity or returns to baseline within 3 weeks of last dose administration:

- If the adverse event has resolved (to  $\leq$  Grade 1 severity or returns to baseline), restart ipilimumab dosing at the next scheduled time point per protocol.
- If the adverse event has not resolved in the protocol-specified dosing window (3 weeks [+/- 3 days], the next scheduled dose will be omitted.
- Patients with Grade 1 diarrhea and/or colitis who require steroid therapy must have resolution to grade 0 (baseline) before resuming dosing with ipilimumab. Patients with Grade  $\geq 2$  related diarrhea and/or colitis must have ipilimumab permanently discontinued (Section [5.5.1.1.3](#)).

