#### 5.5.1.5 **Suggested evaluation and treatment for Immune Related Adverse Events (irAEs) associated with ipilimumab**

**NOTE:** This information has been summarized from the Ipilimumab Investigator Brochure (IB). Please refer to the current version of the IB for more details on the Suggested Work-up and Treatment for irAEs and Management Algorithms. Although these are suggested guidelines that take into consideration potential variations that may be required based on a specific clinical situation, these guidelines are strongly recommended.

Management algorithms for the early detection and treatment of ipilimumab associated toxicities are provided in Appendices [Appendix XII-Appendix XVII](#).

Gastrointestinal (diarrhea) and skin (rash)-related toxicities are the most common irAEs reported in previous studies with ipilimumab. Suggested evaluation procedures for suspected irAEs of the GI tract, liver, skin, eye, pituitary, and adrenal gland are described in the current version of the IB. When symptomatic therapy is inadequate or inappropriate, an irAE should be treated with systemic corticosteroids followed by a gradual taper.

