## E1609 (Arms A and D) GI Management Algorithm

[figure not shown]

\*\* Patients on Arm A and Arm D with Grade 1 diarrhea/colitis must have ipilimumab held until resolution to Grade 0 (baseline) before resuming dosing with ipilimumab. Patients on Arm A and Arm D with Grade 2 diarrhea/colitis must have ipilimumab permanently discontinued.

Patients on IV steroids may be switched to oral corticosteroid (e.g., prednisone) at an equivalent dose at start of tapering or earlier, once sustained clinical improvement is observed. Lower bioavailability of oral corticosteroids should be taken into account when switching to the equivalent dose of PO corticosteroids. Ipilimumab may not be restarted while the patient is being treated with systemic corticosteroids except for patients on stable doses of hormone replacement therapy such as hydrocortisone.

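### Arms A/D (10 mg/kg): Section 5.5.1.1.2 requires return to Grade 0 only for steroid-treated Grade 1 diarrhea/colitis, while the Appendix XIV note requires it for every Grade 1 case

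*Combined protocol and SAP*

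**What the plan says.** Four pieces of current text bear on Grade 1 diarrhea/colitis in Arms A and D.

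- **Order of assessment (5.5.1.1).** For any adverse event the site works stepwise: "First, assess the dose delay criteria and decide whether a scheduled dose should be delayed". The discontinuation criteria come second.
- **Hold (5.5.1.1.1).** Under the heading "Criteria to delay/skip one dose of ipilimumab on Arms A or D (ipilimumab 10 mg/kg"), the first trigger is Grade ≥ "1 diarrhea and/or colitis regardless of attribution".
- **Restart (5.5.1.1.2).** The general rule is "Restart ipilimumab dosing if/when the adverse event(s) resolve(s) to" Grade 1 or less, or baseline. An event that meets this counts as resolved, and the site is to "restart ipilimumab dosing at the next scheduled time point per protocol". If it has not resolved within the dosing window, the next dose is omitted. The third bullet is specific to the bowel: "Patients with Grade 1 diarrhea and/or colitis who require steroid therapy must have resolution to grade 0 (baseline) before resuming dosing with ipilimumab".
- **Algorithm note (Appendix XIV, Arms A and D).** "Patients on Arm A and Arm D with Grade 1 diarrhea/colitis must have ipilimumab held until resolution to Grade 0 (baseline"). Steroids are not mentioned in this sentence.

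Related diarrhea/colitis of Grade 2 or higher is permanently discontinued under 5.5.1.1.3. Section 5.5.1.1.2 repeats this, and the Appendix XIV note agrees for Grade 2. The disagreement therefore concerns Grade 1 only.

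**The concern.** A patient whose Grade 1 diarrhea never needed steroids receives a different instruction depending on which page the site opens. Appendix XIV says to wait for Grade 0. Section 5.5.1.1.2 reserves that requirement for steroid-treated cases and otherwise accepts Grade 1 as good enough to restart.

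What is at stake is whether another 10 mg/kg infusion may be given while mild diarrhea continues. The protocol treats that as a real risk: Section 1.5.4.3 reports cases that began mild and became very severe, and Section 8.1.12 warns that minor diarrhea may signal colitis. The opening note of Section 5.5 says that the 10 mg/kg rules were deliberately tightened because severe toxicity was more frequent there than at 3 mg/kg. A restart rule looser than the arm's own algorithm runs against that intent. It also leaves unclear whether a dose given at Grade 1 was a protocol deviation.

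**Working it through.** No sample size, power or error-rate figure is involved, so the check is a comparison of texts on one test case, followed by a look at who could be affected.

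**Test case.** An Arm A patient with Grade 1 diarrhea persisting at the next scheduled dose, no steroids, baseline Grade 0. Section 3.1.10 excludes patients with frequent diarrhea at baseline, so the return-to-baseline alternative does not normally help.

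| Text | Condition checked | Instruction |
|---|---|---|
| 5.5.1.1.1 | Grade ≥ 1, any attribution: met | Delay |
| 5.5.1.1.2, general rule | At or below Grade 1: met on its face | Restart at next time point |
| 5.5.1.1.2, steroid washout (at least 1 week off) | No steroids given: met | No obstacle |
| 5.5.1.1.2, third bullet | Applies only if steroids were needed: not triggered | Grade 0 not required |
| Appendix XIV, A/D note | Grade 1: met | Hold to Grade 0 |

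Two observations follow.

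1. *Section 5.5.1.1.2 against Appendix XIV.* One limits the Grade 0 requirement to steroid-treated cases; the other, as worded, does not. No ordinary reading makes them say the same thing.
2. *Section 5.5.1.1.2 against 5.5.1.1.1.* The grade that triggers the hold also satisfies the restart threshold. If the hold simply reapplied at every dose, all Grade 1 cases would already need Grade 0, and the steroid qualifier would do nothing.

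**Likely origin (inference).** Arms C/F carry the same restart threshold in 5.5.1.2.2. It fits there, because the non-skin hold in 5.5.1.2.1 starts at Grade 2. The threshold seems not to have been adapted when the A/D bowel hold was lowered to Grade 1. Section 5.5.1.2.2 also sends Grade 2 diarrhea/colitis back to Grade 0 without a steroid condition, so the qualifier is out of step in the stricter arm.

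**Who could be affected.** The stricter A/D plan came with Addendum #7 (marked Rev. 11/13 in Section 5.5). Section 9.10.1 records 405 patients already treated at 10 mg/kg by 9/23/13. With about 500 planned for the arm (Section 9.3), roughly 500 − 405 = 95 came later, plus an unreported number of the 405 still on treatment, plus up to 15 adolescents on Arm D (Section 9.11). The documents do not report how many of these had Grade 1 diarrhea/colitis without steroids.

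**Is anyone still being dosed?** Start window 7 days (5.2.1.1), last dose week 60 with a 2-week visit window (7.2).

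- Adults: 15 Aug 2014 + 7 days + 60 weeks + 2 weeks = 30 Oct 2015.
- Adolescents, if accrual ran to the end of 2016: 31 Dec 2016 + 7 days + 60 weeks + 2 weeks = 17 Mar 2018. If it stopped on 1 Jan 2016, the date is 17 Mar 2017.

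The updated analysis plan in Section 9 refers to September 2018, after these dates. They are not a strict end, because Section 5.2.3 allows further on-protocol ipilimumab after a resected recurrence.

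**The case against.** The best case on the other side is that a careful site would hold the dose anyway. The stepwise order puts the delay criteria first, and a patient with Grade 1 diarrhea on the dosing day meets them. An event that was Grade 1 and stays Grade 1 has arguably not resolved to anything, so the restart rule is never reached. The heading about one dose is generic, is used for Arms C/F too, and sets no limit on how long a hold lasts. The stated aim of a stricter A/D plan points the same way, and Section 5.5.1.1.3 lets the investigator stop for substantial clinical risk.

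Most of this stands. A reader might infer that Section 5.5.1.1 flatly contradicts itself and instructs sites to dose through Grade 1 diarrhea; the documents do not support that. The internal problem is an ambiguity, probably settled in favour of holding.

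It does not dispose of the Appendix XIV conflict. If the algorithm prevails, the third bullet of 5.5.1.1.2 is wrong. If Section 5.5 prevails, the looser wording prevails with it. Section 5.5.1.5 leans towards the second, describing the management guidance thus: "Although these are suggested guidelines that take into consideration potential variations", although it also recommends that guidance strongly. The flow chart that anchors the Appendix XIV note is not shown, so the note's placement cannot be checked; its wording is unconditional.

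**Conclusion.** The point holds as a minor dosing-safety inconsistency: a direct conflict between 5.5.1.1.2 and the Appendix XIV A/D note, and an ambiguity between 5.5.1.1.2 and the Grade ≥ 1 hold in 5.5.1.1.1. It rests on reading the Appendix XIV note as worded, without its figure.

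Its size cannot be put in patients. A reader might take the 10 mg/kg gastrointestinal rates in Section 1.5.4.3 (263/658 of any grade, 83/658 Grade 3–4) and scale the difference to some 500 Arm A patients. That is not supported: the difference mixes Grade 1 with Grade 2, says nothing about steroid use, and would be applied to a cohort of which 405 had been treated before the rule existed.

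Nothing here affects the RFS or OS comparisons, power or type I error. Practical weight is further limited because scheduled dosing has probably ended.

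**What to change.** In the third bullet of 5.5.1.1.2, delete the clause restricting it to patients needing steroids, and exempt diarrhea/colitis from the general restart threshold of Grade 1 or less. All Grade 1 diarrhea/colitis on Arms A and D would then have to return to Grade 0 (baseline) before re-dosing, which matches Appendix XIV and the hold in 5.5.1.1.1.

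If no patient is still receiving ipilimumab, a short clarification stating which rule governed is enough. It would settle whether doses given at Grade 1 count as deviations, and would stop the wording being carried into another protocol.

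The cost is a small text edit or a memo. If anyone is still being dosed, the downside is a few more delayed or omitted infusions.

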#### 5.5.1.1.3

#### **Criteria for permanent discontinuation of ipilimumab for Related Adverse Events on Arms A or D (ipilimumab 10mg/kg)**

Ipilimumab administration must be permanently discontinued for any of the following certainly, probably, or possibly treatment related adverse events, unless otherwise specified:

- Any  $\geq$  Grade 2 eye pain or reduction of visual acuity that does not respond to topical therapy and does not improve to  $\leq$  Grade 1 severity within 2 weeks of starting therapy, OR, requires systemic treatment.
- Any  $\geq$  Grade 2 diarrhea and/or colitis related to ipilimumab. Any  $\geq$  Grade 2 diarrhea/colitis should be considered RELATED unless immune related colitis is definitely ruled out (including by endoscopy and biopsy.)
- Any  $\geq$  Grade 2 hypophysitis, pneumonitis, nephritis, and/or sarcoid-like lesions.
- Any new motor or sensory neurologic toxicity  $\geq$  Grade 2 regardless of attribution (including Guillain-Barré syndrome and myasthenia gravis).
- Any  $\geq$  Grade 3 bronchospasm or other hypersensitivity reaction.

- Any other  $\geq$  Grade 3 non-skin adverse event with the exception of events listed under “Exceptions to Permanent Discontinuation” (Section [5.5.1.1.4](#)).
- AST or ALT  $>$  5 x ULN.
- Total Bilirubin  $>$  3 x ULN.
- Any other  $\geq$  Grade 4 laboratory abnormalities except for specified exceptions (Section 5.5.1.1.4).
- Any other  $\geq$  Grade 4 adverse event.
- Stevens-Johnson syndrome, toxic epidermal necrolysis, or rash complicated by full thickness dermal ulceration or necrotic, bullous, or hemorrhagic manifestations.
- Any adverse event, laboratory abnormality or intercurrent illness which, in the judgment of the investigator, presents a substantial clinical risk to the patient with continued dosing.
- Patients who require high dose steroids, other immune suppressants or anti-TNF drug therapy for the management of immune related adverse events as described in the Toxicity Management Guidelines/Algorithms should have ipilimumab permanently discontinued.

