#### 5.5.1.2.3

#### **Criteria for permanent discontinuation of ipilimumab for Related Adverse Events**

Ipilimumab administration must be permanently discontinued if any of the following Related Adverse Events occurs:

- Any  $\geq$  Grade 2 eye pain or reduction of visual acuity that does not respond to topical therapy and does not improve to  $\leq$  Grade 1 severity within 2 weeks of starting therapy, OR, requires systemic treatment.
- Any  $\geq$  Grade 2 hypophysitis.
- Any  $\geq$  Grade 3 bronchospasm or other hypersensitivity reaction.
- Any other  $\geq$  Grade 3 non-skin related adverse event with the exception of events listed under “Exceptions to Permanent Discontinuation” (Section [5.5.1.2.4](#)).
- Any  $\geq$  Grade 4 laboratory abnormalities, except for specified exceptions (Section [5.5.1.2.4](#)).
- For AST, ALT, or Total Bilirubin, then as follows:
  - AST or ALT  $> 5 \times$  ULN.
  - Total Bilirubin  $> 3 \times$  ULN.
- Any other  $\geq$  Grade 4 adverse event except for specified exceptions (Section [5.5.1.2.4](#)).
- Stevens-Johnson syndrome, toxic epidermal necrolysis, or rash

complicated by full thickness dermal ulceration or necrotic, bullous, or hemorrhagic manifestations.

- Any adverse event, laboratory abnormality or intercurrent illness which, in the judgment of the investigator, presents a substantial clinical risk to the patient with continued dosing.
- Any motor or sensory neurologic toxicity  $\geq$  Grade 3 regardless of attribution.
- Diagnosis with Guillain-Barré syndrome or myasthenia gravis (any grade).
- Patients who require high dose steroids, other immune suppressants or anti-TNF drug therapy for the management of immune related adverse events as described in the Toxicity Management Guidelines/Algorithms should have ipilimumab permanently discontinued. Treatment with oral budesonide or moderate dose steroids for grade 2 colitis or grade 2 or lower skin rash or higher dose IV steroids for grade 3 skin rash are criteria for ipilimumab dose delay but not permanent discontinuation.

Rev. 9/14

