## A Phase III Randomized Study of Adjuvant Ipilimumab Anti-CTLA4 Therapy Versus High Dose Interferon a-2b for Resected High risk Melanoma

### Appendix XIII

#### Suggested Work-up and Treatment for Immune-Related Adverse Events (irAEs)

An IRAE is defined as an adverse event of unknown etiology, associated with drug exposure and is consistent with an immune phenomenon. Efforts should be made to rule out neoplastic, infectious, metabolic, toxin or other etiologic causes prior to labeling an adverse event a non-dermatologic, immune-mediated event. Serological, immunological, and histological (biopsy) data should be used to support the diagnosis of an immune-mediated toxicity. Documentation of test results should be included in the patient's medical record. Effective Amendment #7, the dose delay and discontinuation criteria have been made stricter on Arms A or D (ipilimumab 10 mg/kg) than on Arms C or F (ipilimumab 3 mg/kg) due to a higher incidence of severe toxicities observed on Arms A and D compared to Arms C and F.

Gastrointestinal (diarrhea) and skin (rash)-related toxicities have been the most common IRAEs noted in prior studies with ipilimumab. Suggested work-up procedures for suspected IRAEs of the gastrointestinal tract, liver, skin, eye, pituitary, and adrenal gland are listed below. When symptomatic therapy is inadequate or inappropriate, an IRAE should be treated with steroids followed by a slow taper.

**Gastrointestinal Tract:** Diarrhea (defined as either first watery stool, or increase in frequency 50% above baseline with urgency or nocturnal bowel movement, or bloody stool) should be further evaluated and infectious or alternate etiologies ruled out. Patients should be advised to inform the investigator if any diarrhea occurs, even if it is mild. An algorithm for working up patients with diarrhea or suspected colitis is provided in [Appendix XIV](#).

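### A related Grade 1 Guillain-Barré syndrome or myasthenia gravis is a mandatory permanent stop at 3 mg/kg but meets no diagnosis- or grade-based delay or stop rule at 10 mg/kg

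*Combined protocol and SAP*

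**What the plan says.** The two ipilimumab doses have separate written dose-modification lists.

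- **Status of the lists (5.5.1.1).** For Arms A and D: "The following criteria will be used to determine dosing delay, restarting doses, or discontinuing ipilimumab". Section 5.5.1.2 says the same for Arms C and F.
- **10 mg/kg, permanent stop (5.5.1.1.3).** The neurologic bullet covers new motor or sensory toxicity at or above the stated grade: "Grade 2 regardless of attribution (including Guillain-Barré syndrome and myasthenia gravis". No other bullet in this list names either diagnosis.
- **10 mg/kg, delay (5.5.1.1.1).** The general non-skin rule also begins at or above Grade 2: "Grade 2 non-skin related adverse event (including IRAEs) except for laboratory abnormalities".
- **3 mg/kg, permanent stop (5.5.1.2.3).** The lead-in says that ipilimumab "must be permanently discontinued if any of the following Related Adverse Events occurs". The list includes "Diagnosis with Guillain-Barré syndrome or myasthenia gravis (any grade". A separate bullet stops motor or sensory neurologic toxicity at or above "Grade 3 regardless of attribution".
- **Stated intent.** Section 5.5 says the plan for Arms A and D "has been modified to become stricter due to a higher incidence of severe toxicities observed on Arms A and D". Appendix XIII compares the doses directly: "the dose delay and discontinuation criteria have been made stricter on Arms A or D (ipilimumab 10 mg/kg) than on Arms C or F".

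**The concern.** Elsewhere the neurologic rules at 10 mg/kg are as strict as those at 3 mg/kg or stricter. Here the order is reversed: the diagnosis alone is enough to stop at the lower dose, while the higher-dose list waits for Grade 2. No rationale is given, and the reversal runs against the reason stated for having two lists.

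The protocol treats these diagnoses as serious in their own right. Section 3.1.13 excludes patients with a history of autoimmune motor neuropathy and names both conditions. A footnote to the adverse event list in section 5.4 names both among immune-mediated events that can be severe or fatal. At stake is whether a patient with a new, drug-related, mild case on the higher dose is re-dosed at the investigator's discretion when the lower-dose list would forbid it.

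**Working it through.** No plan figure needs reproducing. The check takes each combination of grade and attribution for these two diagnoses and reads the permanent-stop lists literally.

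**Rules applied**

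- Arms A and D (5.5.1.1.3): stop if Grade 2 or higher, any attribution.
- Arms C and F (5.5.1.2.3): stop if related at any grade (diagnosis bullet), or if Grade 3 or higher at any attribution (motor/sensory bullet).

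| Grade | Attribution | Arms A/D, 10 mg/kg | Arms C/F, 3 mg/kg | Comparison |
|---|---|---|---|---|
| 1 | Related | no stop | stop | reversed |
| 1 | Unrelated | no stop | no stop | equal |
| 2 | Related | stop | stop | equal |
| 2 | Unrelated | stop | no stop | stricter on A/D |
| 3 or higher | Related | stop | stop | equal |
| 3 or higher | Unrelated | stop | stop | equal |

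Count: 1 reversed + 1 stricter on A/D + 4 equal = 6. The tally weights cells equally and says nothing about how often each occurs.

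**Does anything else at 10 mg/kg catch the Grade 1 related case?**

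- Delay list (5.5.1.1.1): non-skin events start at Grade 2, laboratory abnormalities at Grade 2 or 3, and skin events at Grade 3. The only Grade 1 trigger is diarrhea or colitis. Not met.
- Other grade-based stop bullets (5.5.1.1.3): these begin at Grade 2, 3 or 4. Not met.
- Conditional stop bullets (5.5.1.1.3): investigator judgment of substantial clinical risk, or a need for high-dose steroids, other immune suppressants or anti-TNF therapy. Either could apply, but neither is triggered by the diagnosis itself.
- Resumption rule (5.5.1.1.2): bars dosing during oral or intravenous steroid treatment of an immune-related event. This again depends on treatment, not diagnosis.
- Exceptions at 3 mg/kg (5.5.1.2.4): none covers these diagnoses, so the stop there is firm.

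**Frequency.** Section 1.5.4.3 puts each condition under 1% of subjects. Section 5.5.1.5.7 reports three Guillain-Barré cases, two considered study related, with no grades given.

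**Is dosing still under way?** Last planned dose = end of accrual + 7 days to first infusion (5.2.1.1) + 60 weeks (420 days).

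- Adults: 15 August 2014 + 427 days = 16 October 2015.
- Adolescents: section 9.3 says accrual stays open until 2016. Assuming it ended between 1 January and 31 December 2016, the last dose falls between 3 March 2017 and 3 March 2018.
- The visit window can add up to 2 weeks.

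The updated analysis plan at the head of section 9 already describes events as of September 2018. Measured to 1 September 2018, that is about 34.5 months after the last planned adult dose and 6 to 18 months after the last planned adolescent dose.

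**The case against.** The strongest case against has four parts.

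1. **Appendix XVII may close the gap.** It has a separate neuropathy chart for Arms A and D, and that flow chart is not visible in the text available here. Charts in this protocol can carry firm dosing rules. The footnote to the Arms A and D gastrointestinal chart in Appendix XIV requires Grade 1 diarrhea or colitis to resolve to Grade 0 before re-dosing, which is broader than the matching bullet in 5.5.1.1.2. This stands as a limit on what can be claimed, so no mismatch with the chart is alleged. It does not correct the written list, and section 5.5.1.5 describes the algorithms as suggested, though strongly recommended.
2. **The judgment and immunosuppression bullets are themselves written stop criteria.** True, and a mild case might well be stopped through them. But both also appear in the 3 mg/kg list, where the authors still added the any-grade bullet.
3. **A general statement that the rules are stricter need not hold line by line.** This is fair for section 5.5, which describes a change to the 10 mg/kg plan itself. Appendix XIII does compare the doses, and nothing suggests this exception was intended. The parenthesis may have been meant to cover every grade, but as written the Grade 2 threshold governs it.
4. **The events are rare and dosing is almost certainly over.** This stands. It limits the importance of the point, not its correctness.

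**Conclusion.** The inconsistency is real in the written lists and confined to one case: a related Grade 1 Guillain-Barré syndrome or myasthenia gravis. That is one of six combinations. For other motor or sensory toxicity the 10 mg/kg rule is the stricter one, stopping at Grade 2 where 3 mg/kg stops at Grade 3.

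The point is minor. The documents describe no Grade 1 case at either dose, no harm is claimed, and nothing in the statistical analysis is touched. Re-treatment after a resected recurrence is only a narrow remaining route to exposure: section 5.2.3 restarts at the next scheduled dose, and section 8.1.6 caps maintenance at four doses.

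The conclusion rests on a literal reading of the lists. The dosing dates also rest on the assumed 2016 end of adolescent accrual. Whether the Arms A and D chart in Appendix XVII already covers the case is unknown.

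**What to change.** Add to section 5.5.1.1.3, under its existing lead-in for related events, the bullet already used for Arms C and F in section 5.5.1.2.3, which makes a diagnosis of either condition a stop at any grade. Leave the Grade 2 or higher neurologic bullet, with its any-attribution wording, unchanged. Confirm that the Arms A and D neuropathy chart in Appendix XVII agrees.

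With this change the Grade 1 related row becomes a stop at both doses, and the count moves to 0 reversed, 1 stricter on A/D and 5 equal. Nothing is loosened, and no rule is created for unrelated Grade 1 events, which neither list stops now. The cost is one copied bullet and one chart check.
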